7.2.6 Other Procedures

7.2.6.1 Withdrawal/Discontinuation

When a subject discontinues/withdraws prior to trial completion, all applicable activities scheduled for the final trial visit should be performed at the time of discontinuation. Any adverse events which are present at the time of discontinuation/withdrawal should be followed in accordance with the safety requirements outlined below at *Assessing and Recording Adverse Events* (Section 7.3) and then proceed to the *Follow-Up Visits* of the study (Section 7.2.8.).

7.2.7 Visit Requirements

Visit requirements are outlined in Section 7.1 - *Trial Schedule of Events Chart*. Specific procedure-related details are provided above in Section 7.2 - *Trial Procedures*.

7.2.7.1 Screening Period

There will be a screening period of up to 28 days after subjects sign informed consent.

7.2.7.2 Treatment Period

The treatment period is defined as the time that the patients are receiving VESANOID and/or Pembrolizumab treatment.

7.2.7.3 Post-Treatment Visits

7.2.7.3.1 Safety Follow-Up Visits

Subjects who discontinue trial treatment will move into the follow-up phase and other treatment decisions will be at the discretion of the treating physician.

The first safety follow-up visit will be conducted for all subjects 30 days after the last dose of trial treatment (VESANOID and/or pembrolizumab) or before the initiation of a new anti-cancer treatment, whichever comes first.

Should the subject not initiate a new anti-cancer treatment, the second safety follow-up visit will be conducted 90 days after the last dose of trial treatment. All AEs that occur prior to the Safety Follow-Up Visits should be recorded. Subjects with an AE of Grade > 1 will be followed until the resolution of the AE to Grade 0-1 or until the beginning of a new anti-neoplastic therapy, whichever occurs first. SAEs that occur within 90 days of the end of treatment or before initiation of a new anti-cancer treatment should also be followed and recorded.

7.2.7.3.2 Survival Follow-up

Subjects should be contacted at regularly scheduled clinic visits or by telephone every 12 weeks to assess for survival status until death, withdrawal of consent, or the end of the study, whichever occurs first. Every effort should be made to collect information regarding disease status and post-study anti-neoplastic treatment.

Patients will be followed for up to 2 years or until recurrence or death.

7.3 Adverse Events (AE) – Assessing, Recording and Reporting

7.3.1 Definition of AE

An adverse event is defined as any untoward medical occurrence in a patient or clinical investigation subject administered a pharmaceutical product and which does not necessarily have to have a causal relationship with this treatment.

7.3.2 Assessment of AE

An adverse event can therefore be any unfavorable and unintended sign (including an abnormal laboratory finding, for example), symptom, or disease temporally associated with the use of a medicinal product or protocol-specified procedure, whether or not considered related to the medicinal product or protocol-specified procedure. Any worsening (i.e., any clinically significant adverse change in frequency and/or intensity) of a preexisting condition that is temporally associated with the use of the study drug, is also an adverse event.

Adverse events may occur during the course of the use of the study drug in clinical trials, or as prescribed in clinical practice, from overdose (whether accidental or intentional), from abuse and from withdrawal.

Progression of the cancer under study is not considered an adverse event.

7.3.3 Reporting of AEs

All adverse events that occur after the consent form is signed but before treatment allocation must be reported by the investigator if they cause the subject to be excluded from the trial, or are the result of a protocol-specified intervention, including but not limited to washout or discontinuation of usual therapy, diet, placebo treatment or a procedure.

From the time of treatment allocation through 90 days following cessation of treatment, all adverse events must be reported by the investigator. Such events will be recorded at each examination on the adverse event case report forms/worksheets. The reporting timeframe for adverse events meeting any serious criteria is described in Section 7.4 (*Serious Adverse Events (SAE) – Assessing, Recording and Reporting*). The investigator will make every attempt to follow all subjects with non-serious adverse events for outcome.

7.4 Serious Adverse Events (SAE) – Assessing, Recording and Reporting

7.4.1 Definition and Assessment SAEs

A serious adverse event is any adverse event occurring at any dose or during any use of Pembrolizumab and VESANOID that:

- Results in death;
- Is life threatening;
- Results in persistent or significant disability/incapacity;
- Results in or prolongs an existing inpatient hospitalization;
- Is a congenital anomaly/birth defect;
- Is another important medical event.

Refer to Table 6 for additional details regarding each of the above criteria.

7.4.2 Immediate Reporting of SAEs

For the time period beginning when the consent form is signed until treatment allocation, any serious adverse event, or follow up to a serious adverse event, including death due to any cause other than progression of the cancer under study (reference section 7.4.3 below - *Protocol Specific Exceptions to Serious Adverse Event Reporting* for additional details) that occurs to any subject must be reported within 24 hours to the Sponsor-Investigator, within 2 business days to Merck Global Safety (Attn: Worldwide Product Safety; [contact]), within 5 business days to the DSMC, and in accordance with COMIRB reporting requirements (within 5 business days or during continuing review) if it causes the subject to be excluded from the trial, or is the result of a protocol-specified intervention, including but not limited to washout or discontinuation of usual therapy, diet, placebo treatment or a procedure.

For the time period beginning at treatment allocation through 90 days following cessation of treatment, or 30 days following cessation of treatment if the subject initiates new anticancer therapy, whichever is earlier, any serious adverse event, or follow up to a serious adverse event, including death due to any cause other than progression of the cancer under study (reference section 7.4.3 below - *Protocol Specific Exceptions to Serious Adverse Event Reporting* for additional details), whether or not related to the study drug, must be reported within 24 hours to the Sponsor-Investigator, within 2 business days to Merck Global Safety, within 5 business days to the DSMC, and in accordance with COMIRB reporting requirements (within 5 business days or during continuing review).

Additionally, any serious adverse event, considered by an investigator who is a qualified physician to be related to the study drug, that is brought to the attention of the investigator at any time following consent through the end of the specified safety follow-up period specified in the paragraph above, or at any time outside of the time period specified in the previous paragraph also must be reported within 24 hours to the Sponsor-Investigator, within 2 business days to Merck Global Safety, within 5 business days to the DSMC, and in accordance with COMIRB reporting requirements (within 5 business days or during continuing review).

All subjects with serious adverse events must be followed up for outcome.

7.4.3 Protocol-Specific Exceptions to Serious Adverse Event Reporting

The suspected/actual events covered in this exception include any event that is disease progression of the cancer under study. Additionally, hospitalization related to convenience (e.g., transportation issues etc.) will not be considered a SAE.

7.5 Events of Clinical Interest (ECI)

Selected non-serious and serious adverse events are also known as Events of Clinical Interest (ECI) and must be reported be within 24 hours to the Sponsor-Investigator, within 2 working

days to Merck Global Safety, within 5 business days to the DSMC, and in accordance with COMIRB reporting requirements (within 5 business days or during continuing review).

For the time period beginning when the consent form is signed until treatment allocation, any ECI, or follow up to an ECI, that occurs to any subject must be reported within 24 hours to the investigator if it causes the subject to be excluded from the trial, or is the result of a protocol-specified intervention, including but not limited to washout or discontinuation of usual therapy, diet, placebo treatment or a procedure.

For the time period beginning at treatment allocation through 90 days following cessation of treatment, or 30 days following cessation of treatment if the subject initiates new anticancer therapy, whichever is earlier, any ECI, or follow up to an ECI, must be reported within 24 hours to the Sponsor-Investigator, within 2 working days to Merck Global Safety, within 5 business days to the DSMC, and in accordance with COMIRB reporting requirements (within 5 business days or during continuing review).

Events of clinical interest for this trial include:

1. An elevated AST or ALT lab value that is greater than or equal to 3X the upper limit of normal and an elevated total bilirubin lab value that is greater than or equal to 2X the upper limit of normal and, at the same time, an alkaline phosphatase lab value that is less than 2X the upper limit of normal, as determined by way of protocol-specified laboratory testing or unscheduled laboratory testing.*

*Note: These criteria are based upon available regulatory guidance documents. The purpose of the criteria is to specify a threshold of abnormal hepatic tests that may require an additional evaluation for an underlying etiology.

7.6 Reporting of Pregnancy and Lactation

Although pregnancy and lactation are not considered adverse events, it is the responsibility of investigators or their designees to report any pregnancy or lactation in a subject (spontaneously reported to them) that occurs during the trial.

Pregnancies and lactations that occur after the consent form is signed but before treatment allocation must be reported by the investigator if they cause the subject to be excluded from the trial, or are the result of a protocol-specified intervention, including but not limited to washout or discontinuation of usual therapy, diet, placebo treatment or a procedure.

Pregnancies and lactations that occur from the time of treatment allocation through 120 days following cessation of the study drugs, or 30 days following cessation of treatment if the subject initiates new anticancer therapy, whichever is earlier, must be reported by the investigator. All reported pregnancies must be followed to the completion/termination of the pregnancy. Pregnancy outcomes of spontaneous abortion, missed abortion, benign hydatidiform mole, blighted ovum, fetal death, intrauterine death, miscarriage and stillbirth must be reported as serious events (Important Medical Events). If the pregnancy continues

to term, the outcome (health of infant) must also be reported. Such events must be reported within 24 hours to the Sponsor-Investigator, within 2 working days to Merck Global Safety. (Attn: Worldwide Product Safety; [contact]), within 5 days to the DSMC and within 5 days to COMIRB.

7.7 Sponsor-Investigator Responsibility for Reporting Adverse Events

The Sponsor-Investigator will report all Adverse Events to regulatory authorities and COMIRB, in accordance with all applicable laws and regulations.

7.7.1 Evaluating Adverse Events

An investigator who is a qualified physician will evaluate all adverse events according to the NCI Common Terminology for Adverse Events (CTCAE), version 4.0. Any adverse event which changes CTCAE grade over the course of a given episode will have each change of grade recorded on the adverse event case report forms/worksheets.

All adverse events regardless of CTCAE grade must also be evaluated for seriousness.

Table 6 Evaluating Adverse Events

An investigator who is a qualified physician, will evaluate all adverse events as to:

V4.0 CTCAE Grading	Grade 1	Mild; asymptomatic or mid symptoms; clinical or diagnostic observations only; intervention not indicated.						
	Grade 2	Moderate; minimal, local or noninvasive intervention indicated; limiting age-appropriate instrumental ADL.						
	Grade 3	Severe or medically significant but not immediately life-threatening; hospitalization or prolongation or hospitalization indicated; disabling; limiting self-care ADL.						
	Grade 4	Life threatening consequences; urgent intervention indicated.						
	Grade 5	Death related to AE						
Seriousness	A serious adverse event is any adverse event occurring at any dose or during any use of study drug product that:							
	†Results in death; or							
	† Is life threatening; or places the subject, in the view of the investigator, at immediate risk of death from the event as it occurred (Note: This does not include an adverse event that, had it occurred in a more severe form, might have caused death.); or							
	†Results in a persistent or significant disability/incapacity (substantial disruption of one's ability to conduct normal life functions); or							
	†Results in on hospitalization worsened is no patient's medi	prolongs an existing inpatient hospitalization (hospitalization is defined as an inpatient admission, regardless of length of stay, even if the is a precautionary measure for continued observation. (Note: Hospitalization for an elective procedure to treat a pre-existing condition that has not a serious adverse event. A pre-existing condition is a clinical condition that is diagnosed prior to the use of study drug and is documented in the cal history.); or						

	†Is a congenital	Is a congenital anomaly/birth defect (in offspring of subject taking the product regardless of time to diagnosis);or									
	Is a new cancer working days to	Is a new cancer (that is not a condition of the study) (although not serious per ICH definition, is reportable to the investigator within 24 hours and to Merck within 2 working days to meet certain local requirements); or									
	Is an overdose (whether accidental or intentional). Any adverse event associated with an overdose is considered a serious adverse event for collection purposes. overdose that is not associated with an adverse event is considered a non-serious event of clinical interest and must be reported within 24 hours to the investigator to Merck Global Safety, the DSMC, and COMIRB within 2 working days.										
	Other important medical events that may not result in death, not be life threatening, or not require hospitalization may be considered a serious adverse event when, based upon appropriate medical judgment, the event may jeopardize the subject and may require medical or surgical intervention to prevent one of the outcomes listed previously (designated above by a [†]).										
Duration	Record the start	Record the start and stop dates of the adverse event. If less than 1 day, indicate the appropriate length of time and units									
Action taken	Did the adverse event cause study drug to be discontinued?										
Relationship to Study Drug	Did study drug c qualified physici medically qualifi intended as refer available informa	Did study drug cause the adverse event? The determination of the likelihood that study drug caused the adverse event will be provided by an investigator who is a qualified physician. The investigator's signed/dated initials on the source document or worksheet that supports the causality noted on the AE form, ensures that a medically qualified assessment of causality was done. This initialed document must be retained for the required regulatory time frame. The criteria below are intended as reference guidelines to assist the investigator in assessing the likelihood of a relationship between the test drug and the adverse event based upon the available information.									
	The following correspective eleme	The following components are to be used to assess the relationship between study drug and the AE; the greater the correlation with the components and their respective elements (in number and/or intensity), the more likely study drug caused the adverse event (AE):									
	Exposure Is there evidence that the subject was actually exposed to study drug such as: reliable history, acceptable compliance assessment (pill count, diary, etc.), expected pharmacologic effect, or measurement of drug/metabolite in bodily specimen?										
	Time Course Did the AE follow in a reasonable temporal sequence from administration of Merck product? Is the time of onset of the AE compatible with a drug-induced effect (applies to trials with investigational medicinal product)?										
	Likely Cause	Is the AE not reasonably explained by another etiology such as underlying disease, other drug(s)/vaccine(s), or other host or environmental factors									

Relationship	The following components are to be used to assess the relationship between the test drug and the AE: (continued)							
to Study Drug	Dechallenge	Was study drug discontinued or dose/exposure/frequency reduced?						
(continued)		If yes, did the AE resolve or improve?						
		If yes, this is a positive dechallenge. If no, this is a negative dechallenge.						
		(Note: This criterion is not applicable if: (1) the AE resulted in death or permanent disability; (2) the AE resolved/improved despite continuation of the Sponsor's product; or (3) the trial is a single-dose drug trial); or (4) Sponsor's product(s) is/are only used one time.)						
	Rechallenge	Was the subject re-exposed to study drug in this study?						
		If yes, did the AE recur or worsen?						
		If yes, this is a positive rechallenge. If no, this is a negative rechallenge.						
		(Note: This criterion is not applicable if: (1) the initial AE resulted in death or permanent disability, or (2) the trial is a single-dose drug trial); or (3) Sponsor's product(s) is/are used only one time).						
		NOTE: IF A RECHALLENGE IS PLANNED FOR AN ADVERSE EVENT WHICH WAS SERIOUS AND WHICH MAY HAVE BEEN CAUSED BY STUDY DRUG, OR IF REEXPOSURE TO STUDY DRUG POSES ADDITIONAL POTENTIAL SIGNIFICANT RISK TO THE SUBJECT, THEN THE RECHALLENGE MUST BE APPROVED IN ADVANCE BY THE SPONSOR AS PER DOSE MODIFICATION GUIDELINES IN THE PROTOCOL.						
	Consistency with Trial Treatment Profile	Is the clinical/pathological presentation of the AE consistent with previous knowledge regarding study drug or drug class pharmacology or toxicology?						
The assessment of consideration of the	relationship will be above elements.	be reported on the case report forms /worksheets by an investigator who is a qualified physician according to his/her best clinical judgment, including						
Record one of the	e following	Use the following scale of criteria as guidance (not all criteria must be present to be indicative of Merck product relationship).						
Yes, there is a rea possibility of Mer relationship.	asonable rck product	There is evidence of exposure to Merck product. The temporal sequence of the AE onset relative to the administration of Merck product is reasonable. The AE is more likely explained by Merck product than by another cause.						
No, there is not a possibility of Mer relationship	reasonable rck product	Subject did not receive the Merck product OR temporal sequence of the AE onset relative to administration of Merck product is not reasonable OR the AE is more likely explained by another cause than the Merck product. (Also entered for a subject with overdose without an associated AE.)						

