The trial stopping criteria outlined in the table found in Section 6.6.5 - *Toxicity and Study Discontinuation Criteria* will be followed to avoid posing undue risk to additional patients. Twenty four (24) patients will potentially be recruited to further evaluate safety and assess preliminary efficacy.

Dose limiting toxicities are defined according to the AE profile observed during the first cycle (Cycle 1 Day 0 to Cycle 2 Day 0) of study drug administration. All AEs should be considered possibly related to the study drug unless such relationship can be definitively excluded.

Toxicity will be evaluated according to NCI CTCAE Version 4.0. A DLT will be defined as any of the following events that are considered by the investigator to be at least possibly related to treatment with Vesanoid and Pembrolizumab:

- 1. Any >= grade 3 non-hematologic toxicity related to VESANOID, > = grade 4 hematologic toxicity related to VESANOID or other grade VESANOID related adverse events that lead to treatment discontinuation. An exception is VESANOID related headache not optimally managed with supportive care therapies (acetaminophen or non-steroidal antiinflammatory medication) or that does not resolve within 72 hours of stopping the VESANOID. A patient's choice to stop all VESANOID, with or without a dose reduction, due to headache alone will not be considered a dose limiting toxicity.
- 2. Any >= grade 3 toxicity related to Pembrolizumab.

Dose Level	Number of Patients	Vesanoid	Pembrolizumab
-1	6	$100 \text{ mg/m}^2 \text{ PO on days -1, 0, and 1}$ every 3 weeks for the first 4 cycles	200 mg IV on Day 0 every 3 weeks
1 (Starting Dose)	6	150 mg/m ² PO on days -1, 0, and 1 every 3 weeks for the first 4 cycles	200 mg IV on Day 0 every 3 weeks

The dose levels will be as follows:

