8.0 STATISTICAL ANALYSIS PLAN

The primary goal of the study is to characterize the safety and establish the recommended phase 2 dose (RP2D) and preliminary efficacy evaluation with a total of 24 evaluable subjects. A modified 3+3 design with a cohort size of 6 with a continuous toxicity monitoring. The design is to inform de-escalation decisions based on safety if needed. For the purposes of this trial, a target toxicity rate of approximately 33% will be used to establish the RP2D. Table 7 below provides the probability of detecting the number of DLTs based on true toxicity rates with 24 subjects:

Table 7 Number of DLTs and the Corresponding Cumulative Probability for SeveralToxicity Rates with 24 Subjects

True toxicity rate (%)	Corresponding Number of	Cumulative Probability for
	DLTs (# DLT)	Detecting #DLT
20	5	0.66
25	6	0.56
30	7	0.56
35	8	0.53
40	10	0.65

Safety Analyses

All patients who received any protocol therapy will be employed for safety analyses. Patient incidence of all treatment-emergent AEs will be tabulated by dose and system organ class and preferred term. Tables of fatal adverse events, serious adverse events, treatmentrelated AEs, and adverse events leading to withdrawal from investigation product will also be provided. The MedDRA will be used to code adverse events and the NCI CTCAE version 4.0 will be used to grade severity of adverse events and laboratory toxicities.

Summary statistic will be provided for total number of subjects treated under each dose, average dose administered, and duration of treatment.

For select laboratory parameters, changes of laboratory values over time (eg, change from baseline summary statistics), grade shifts in laboratory values from baseline to worst onstudy value, and grade 3 or higher laboratory toxicities will be summarized. The ECG measurements from this study will be performed as per standard of care for routine safety monitoring.

Efficacy analysis

The efficacy analysis population consists of all subjects who receive at least one cycle treatment (3-day doses of study treatment).

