9.0 LABELING, PACKAGING, STORAGE AND RETURN OF CLINICAL SUPPLIES

9.1 Investigational Product

VESANOID will be supplied through the University of Colorado Cancer Center's investigational pharmacy. VERSANOID is supplied as 10 mg capsules, two-tone (lengthwise), orange-yellow and reddish-brown and imprinted VERSANOID 10 ROCHE. It is packaged in high-density polyethylene opaque bottles of 100 capsule with child-resistance closure.

Pembrolizumab (200mg dosing Q3 weeks) will be supplied by Merck.

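### Table 6 records causality for the Merck product only, so the treatment-related AE table may under-count VESANOID toxicity

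*Combined protocol and SAP*

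**What the plan says.** The causality block of Table 6 (Section 7.7.1) is headed as relationship to study drug and opens with the question "Did study drug cause the adverse event"? Its closing rows, which give the answers to be entered on the case report forms or worksheets, change the subject. Each answer is about whether there is a reasonable possibility of a relationship to the Merck product. The guidance for Yes includes "The AE is more likely explained by Merck product than by another cause". The guidance for No is a list joined by OR, whose last clinical ground is that "the AE is more likely explained by another cause than the Merck product". The criteria are introduced with "Use the following scale of criteria as guidance (not all criteria must be present to be indicative of Merck product relationship", and the answer is left to the investigator's clinical judgment.

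Section 9.1 shows which drug is the Merck product: "Pembrolizumab (200mg dosing Q3 weeks) will be supplied by Merck", whereas "VESANOID will be supplied through the University of Colorado Cancer Center's investigational pharmacy". Table 2 (Section 6.1) lists pembrolizumab as the standard agent and all-trans retinoic acid as the experimental agent.

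For DLTs, Section 6.1.1.2.3 says: "All AEs should be considered possibly related to the study drug unless such relationship can be definitively excluded". It then defines a DLT as an event at least possibly related to treatment, with one item for VESANOID-related toxicity and one for pembrolizumab-related toxicity.

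Among its safety outputs the SAP (Section 8.0) lists "Tables of fatal adverse events, serious adverse events, treatmentrelated AEs". It does not define treatment-related.

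**The concern.** The trial adds VESANOID to a standard drug, so the safety question is what VESANOID contributes. The only causality answer that the protocol specifies for recording names the other drug. If sites follow the wording, an event that the investigator attributes to VESANOID is stored as not related. A treatment-related AE table built from that field would then describe pembrolizumab toxicity under a title that readers will take to cover the combination.

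The threshold is a second, smaller problem. The label asks about a reasonable possibility, while the criterion under it asks whether the product is the more likely cause. Two investigators could record the same uncertain event differently, depending on which line they follow.

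**Working it through.** The plan states no figure on this point, so the check sets the texts side by side.

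**Step 1: which drug is the Merck product?** Section 9.1 has Merck supplying pembrolizumab. VESANOID comes from the cancer center's investigational pharmacy, in capsules imprinted ROCHE. The Merck product is therefore pembrolizumab alone.

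**Step 2: apply the closing rows of Table 6 literally.**

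| Investigator's view of the cause | Answer under the closing rows | What the record then shows |
|---|---|---|
| Pembrolizumab alone | Yes | Related |
| VESANOID alone | No (another cause is more likely) | Not related |
| Neither drug | No | Not related |
| Both drugs, or cannot tell | Depends on which line is followed | Unclear |

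The second and third rows give the same record. Because the grounds for No are joined by OR, the single ground about another cause is enough. The Likely Cause component of the same table supports this reading, since it counts other drugs among the alternative explanations. The Time Course component also asks about the Merck product.

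**Step 3: compare the thresholds.** Four wordings are in use, from widest to narrowest:

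1. Section 6.1.1.2.3, default: related unless definitively excluded.
2. Section 6.1.1.2.3, DLT definition: at least possibly related.
3. Table 6, answer label: reasonable possibility.
4. Table 6, criterion under that label: more likely than another cause.

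Items 3 and 4 belong to the same answer and disagree. As an illustration, take an event that the investigator thinks is 30% likely to be due to the drug. It can fairly be called a reasonable possibility, yet it fails a more-likely-than-another-cause test.

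**Step 4: find the outputs that need this field.** The SAP lists tables of all treatment-emergent AEs by dose, fatal AEs, serious AEs, treatment-related AEs, and AEs leading to withdrawal. Only the treatment-related table depends on attribution by its name. The SAP gives no source for it, and Table 6 is the only recorded causality answer that the protocol specifies.

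**The case against.** The strongest reply is that the closing rows are loosely adapted template text, not a rule that excludes VESANOID. The block is headed by study drug. The Exposure, Dechallenge, Rechallenge and Consistency components also ask about study drug, and other terms (test drug, Sponsor's product) appear in the same table. The SAE definition in Section 7.4.1 covers both drugs. The criteria are guidance, and the principal investigator and treating team are to judge VESANOID's contribution to AEs (Section 6.1.1.2.3). The CRF is not in the documents and may already have a VESANOID field. All of this stands as a reason to speak of a risk and not of an error that has occurred. It does not remove the defect: the answers offered still name one product, and the VESANOID judgment in Section 6.1.1.2.3 has no recorded category.

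A reader might infer that the DLT counts, and so the RP2D, are also wrong. The documents do not support that. Section 6.1.1.2.3 gives DLTs their own definition, separate for each drug and on the broader standard, and nothing derives them from the Table 6 answer. Lost attribution would matter if it did reach the DLT count. With a true DLT rate of 33%, the binomial chance of 3 or more DLTs in 6 is 0.313. If 25% of DLTs went unattributed (an assumption), the rate would be 0.33 × 0.75 = 0.2475 and the chance 0.166. But the documents give no such fraction, and the DLT definition itself implies none.

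A reader might also size the problem from the 86% headache rate in Section 6.1.1.2.2 (0.86 × 24 = 20.6 patients). That rate comes from APL patients, covers any grade, and is stated regardless of drug relationship. It is not a rate of VESANOID-caused events in this trial.

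Finally, applying the definitively-excluded presumption to every AE would class most events as related to both drugs and leave the table with little to show. A cautious DLT screen and a general causality assessment may reasonably differ, so that presumption need not be carried over.

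**Conclusion.** The point holds in a limited form. As written, the recorded causality answer covers pembrolizumab only and enters a VESANOID-only event as No, and its criterion is stricter than its label. The exposed result is one SAP output, the treatment-related AE table, which may under-count VESANOID toxicity. The tables of all treatment-emergent, fatal and serious AEs do not depend on this field, and DLT counts are not shown to be affected.

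No number can be put on the under-count. It would consist of the events attributed to VESANOID alone, plus some share of those attributed to both drugs or to neither with confidence. The conclusion rests on two assumptions: that sites follow the closing rows of Table 6 as worded, and that the CRF mirrors them.

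**What to change.** - In Table 6 and the matching CRF field, replace the two Merck-product answers with two answers per AE: relationship to VESANOID (Yes/No) and relationship to pembrolizumab (Yes/No).
- Replace the remaining Merck-product wording in the causality block, such as that under Time Course, with the name of the drug being assessed.
- Reword the criterion so that it matches the reasonable-possibility label, and reconcile it with the at-least-possibly-related wording in Section 6.1.1.2.3. If the general assessment and the DLT screen are meant to differ, say so.
- In SAP Section 8.0, define treatment-related as related to either drug, name the fields used, and tabulate by drug as well as overall.

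The cost is one extra CRF field, short text changes in Table 6 and the SAP, and more AEs classed as related than under the present wording. Sample size, dosing rules and visit schedule do not change.
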